Each subject will be randomized to a treatment arm using a randomization website (www.random.org). When subjects have multiple teeth eligible for the study, a separate randomization scheme (also from www.random.org) will be used to select that tooth. A printout of the randomization scheme will be used by the investigator distributing the products.

Blinding

Examiners collecting the sensitivity data will be blinded as to which group the subject is in. An investigator who did not examine the subject will distribute the product.

C) Products

Group	Product 1	Product 2
Group I (Control)	Sensodyne (Potassium Nitrate) manufactured by GalaxoSmithKline	N/A
Group II	Crest Cavity Protection manufactured by Procter and Gamble	MI Paste Plus (CPP-ACP with fluoride) manufactured by GC America
Group III	Clinpro 5000 (5000ppm NaF with TCP) manufactured by 3M ESPE	N/A

Sensodyne is FDA approved for decreasing tooth sensitivity. It is approved for use as it is being used this study.

Clinpro 5000 has been FDA approved for the prevention or reduction of dental caries. A reduction in dentinal hypersensitivity has been anecdotally documented in the literature.

MI Paste Plus is FDA approved for the reduction of dentinal hypersensitivity. It is approved for use as it is being used this study.

Crest Cavity Protection Toothpaste is FDA approved as an anticavity drug.

Oral-B 35 soft manual toothbrush is FDA approved and being used as approved for this study.

All products are being used according to manufacturer's instructions.

D) Subject Characteristics

1) Inclusion Criteria

- At least 18 years of age
- Tooth with exposed root surface and/or exposed dentin
- Tooth with a VAS score greater than or equal to 3
- No adjacent tooth/teeth with sensitivity (as defined as greater than 2 on the VAS)

2) Exclusion Criteria

- Participation in another dental study that may alter the results of this study.
- A medical condition that could interfere with reliable pain reporting (e.g., pain disorders)
- Any chronic medical condition that requires the regular use of pain or anti-inflammatory medications
- Used a desensitizing dentifrice within the preceding four weeks
- Have received an antihypersensitivity treatment (varnish or precipitating solution) of the identified tooth within the preceding four weeks
- Undergoing active orthodontic treatment.

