- Teeth with carious lesions, buccal vertical cracks in enamel, evidence of irreversible pulpitis (pain lasting more than five seconds after air stimulation)
- Pregnant/ lactating patients (Clinpro5000 has 5000ppm fluoride and there is a risk of ingesting the product)
- Patients with Milk Allergy (CPP-ACP is a dairy based product)
- Patients on Kidney Dialysis (due to the free calcium in CPP-ACP, dialysis patients should be on a diet with limited calcium)

3) Subject Withdrawal/Termination Criteria

- Subjects will be withdrawn from the study if they report the use of other dental hygiene products, including but not limited to: toothpaste, rinses, fluoride varnishes

- Subjects will be withdrawn from the study if they undergo any phase I periodontal procedures, including a prophylaxis or scaling and root planing
- Subjects would be withdrawn if they experience a negative side effect from any product used in the study.
- The tooth being studied is extracted, damaged from trauma or receives endodontic therapy.
- Subjects may participate in another research study at the same time, as long as it does not impact the results from this study.
- Subjects who do not comply with the study procedures, such as not returning for visits, not using product as documented in diary, may be withdrawn from the study.
- Subjects who become pregnant during the course of the study will be withdrawn. Subjects will be informed in the informed consent form to inform principal investigator or their designate if they become pregnant.
- Subjects who decide to stop participating in the study will be withdrawn.

The Principal Investigator will determine whether subjects (either withdrawn subjects or subjects completing the study) are in need of additional treatment and/or follow-up observation as a result of participation in this trial.

E) Assessment

1) Risk

This study poses minimal risk to subjects as these are products that are approved for use.

With Clinpro5000, although the patient will be instructed not to ingest the product, ingestion may result in GI discomfort, nausea, vomiting, diarrhea, cramping and fluorosis in children. Fluoride exposure should be monitored in pregnant and nursing women. Pregnant and lactating women and children will be excluded from this study.

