Air test: A 1 second blast of air from an air-water syringe that is set to 45psi at a distance of 10mm will be applied to the tooth. Adjacent teeth will be protected with fingers or cotton rolls. The subject will classify the extent of the sensitivity on the VAS. If the discomfort becomes intolerable, the stimulus will be immediately removed.

Water test: The patient will be given a 5-minute rest between tests. Disposable, plastic syringes filled with water will be kept in an ice water bath until use. Then, cold water will be applied to tooth using a plastic syringe with a plastic tip. Three drops of water will be placed on the tooth¹⁶. Adjacent teeth will be protected with fingers or cotton rolls. The subject will classify the extent of the sensitivity on the VAS. If the discomfort becomes intolerable, the stimulus will be immediately removed.

Schiff Test: The Schiff Sensitivity Scale²¹ will be utilized by the examiners to evaluate the response of the subjects to both the air and water test. This analog scale scores for the tooth as 0, 1, 2 or 3.

0-Tooth/Subject does not respond to stimulus.

1-Tooth/Subject responds to stimulus, but does not request discontinuation of stimulus.

2-Tooth/Subject responds to stimulus and requests discontinuation or moves from stimulus.

3-Tooth/Subject responds to stimulus, considers stimulus to be painful, and requests discontinuation of the stimulus

If the subject qualifies for the study, they will be entered into randomization.

Intraoral photographs of the study teeth will be taken. Photographs are for research purposes. Photographs will be taken at Visits 1 and 4. Additional photographs may be taken to document any adverse reactions.

After taking the data, the examiner will leave the operatory and another study team member will do the randomization. In this way the examiner will be blinded as to which group the subject is a part of.

Subject will be randomized to one of three groups:

Group I: Control

The control group will use Sensodyne toothpaste twice daily (2 minutes each time in the morning and the evening) during the duration of the study.

Group II:

Subjects will be instructed to brush twice daily (2 minutes each time in the morning and the evening) using Crest Cavity Protection toothpaste. They will be instructed to apply MI Paste Plus (CPP-ACP with fluoride) twice daily to the study teeth after brushing their teeth. MI Paste Plus will be applied to the study teeth with a finger.

Group III:

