Subjects will be instructed to brush twice daily (2 minutes each time in the morning and the evening) using Clinpro 5000 (5000ppm NaF with TCP).

The study team member will describe the proper use for the products and will review oral hygiene instructions. Once the subject demonstrates understanding for the use of the products, the products and a handout for the use of the products will be distributed. A toothbrush and 2-minute timer will also be given to the subject. The use of any other topical dental products (e.g., rinses, toothpastes, fluoride varnish) will be discontinued. The subjects may use additional products (e.g., dental floss, interproximal devices) to remove plaque. Subjects will be given a diary in which to track product usage. Diary is for research purposes.

Visit 2 (2 weeks +/- 2 days after Visit 1):

A study team member who did not examine the subject at the initial visit will ask the subject for any changes in the medical or dental history. The study team member will also discuss patient compliance, adverse events, review and collect the patient's diary, hand out a new patient diary, and answer any questions that the subject has regarding the products and dispense additional products, if necessary.

Eligibility and subject withdrawal criteria will be reviewed to ensure the subject still qualifies for the study.

The same examiner from the initial visit will then conduct the oral exam and collect the sensitivity data (if necessary, another examiner may see the subject, however, this will be avoided if possible).

An oral exam, including evaluation of oral cavity and soft tissues, will be completed following standard of care procedures.

The same sensitivity tests will be done as at Visit 1. Tests are for research purposes.

Visit 3 (4 weeks +/- 2 days after Visit 1):

A study team member who did not exam the subject at the initial visit will ask the subject for any changes in the medical or dental history. The study team member will also discuss patient compliance, adverse events, review and

collect the patient's diary, hand out a new patient diary, answer any questions that the subject has regarding the products.

Eligibility and subject withdrawal criteria will be reviewed to ensure the subject still qualifies for the study.

The same examiner from the initial visit will then conduct the oral exam and collect the sensitivity data (if necessary, another examiner may see the subject, however, this will be avoided if possible).

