An oral exam, including evaluation of oral cavity and soft tissues, will be completed following standard of care procedures.

The same sensitivity tests will be done as at Visit 1. Tests are for research purposes.

Visit 4 (8 weeks +/- 1 week after Visit 1):

A study team member who did not exam the subject at the initial visit will ask the subject for any changes in the medical or dental history. The study team member will also discuss patient compliance, adverse events, review and collect the patient's diary, answer any questions that the subject has regarding the products.

Eligibility and subject withdrawal criteria will be reviewed to ensure the subject still qualifies for the study.

The same examiner from the initial visit will then conduct the oral exam and collect the sensitivity data (if necessary, another examiner may see the subject, however, this will be avoided if possible).

An oral exam, including evaluation of oral cavity and soft tissues, will be completed following standard of care procedures.

The same sensitivity tests will be done as at Visit 1. Tests are for research purposes.

Intraoral photographs will be taken of the study teeth. Photographs are for research purposes.

All products may be kept by the subject at the end of the study.

Subject timeline

Procedures	Appointment	Visit 1 Screening/ Baseline	Visit 2 (Treatment Day 14)	Visit 3 (Treatment Week 4)	Visit 4 (Treatment Week 8)
Informed Consent	X				
Demographics	X				X
Medical/Dental History	X	X	X	X	X
Evaluate Eligibility and Subject Withdrawal Criteria	X	X	X	X	X
Oral Examination	X	X	X	X	X
Subject VAS Score (Air/Cold Water)	X	X	X	X	X
Examiner Schiff Sensitivity Scale	X	X	X	X	X
Digital Intraoral Photographs	X				X
Assignment into Study Group	X				
Adverse Event Assessment		X	X	X	X
Handout Diary	X	X	X		
Collect Diary		X	X	X	
Stipend	X	X	X	X	X

G) Subject Safety

1) Adverse Event Reporting

Adverse Events

An adverse event is any untoward or unfavorable medical occurrence in a human subject, including any abnormal physical exam or laboratory finding, symptom, or disease, temporally associated with a subject's participation in the research.

Adverse events will be recorded in source documents and on case report forms. All adverse events and non-serious situations will be recorded, monitored, and reported to the IRB at time of continuing review.

Serious Adverse Events

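### Does the eligibility review at Visits 2 to 4 remove adherent controls, or subjects whose tooth improves below VAS 3?

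*Combined protocol and SAP*

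**What the plan says.** Section III.F repeats one sentence at each of the three follow-up visits: "Eligibility and subject withdrawal criteria will be reviewed to ensure the subject still qualifies for the study". The subject timeline carries the same item as a single row, "Evaluate Eligibility and Subject Withdrawal Criteria".

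Two criteria in III.D matter here, and neither carries a time limit. The inclusion list (III.D.1) requires "Tooth with a VAS score greater than or equal to 3". The exclusion list (III.D.2) names anyone who "Used a desensitizing dentifrice within the preceding four weeks".

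For the control arm, III.F states "The control group will use Sensodyne toothpaste twice daily" for the duration of the study. III.C describes that product as approved for decreasing tooth sensitivity.

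Withdrawal has its own list in III.D.3. It includes "Subjects will be withdrawn from the study if they report the use of other dental hygiene products", and it says that subjects who do not comply, for example by "not using product as documented in diary, may be withdrawn from the study". It mentions neither a VAS score below 3 nor use of the assigned toothpaste.

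**The concern.** The review sentence names eligibility and withdrawal criteria separately, so it is not simply a reference to the withdrawal list. Asking whether a subject still qualifies reads like the entry test applied again.

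On that reading there are two problems:

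- **Dentifrice criterion.** Visit 2 falls two weeks after the start, inside the four-week look-back. Every control who uses the assigned product fails. A control who does not use it may be withdrawn for non-compliance.
- **VAS criterion.** VAS is the outcome measure. Removing subjects below 3 removes those who responded best, and more of them in the test arms.

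Removal after randomization that depends on arm or on response would bias the comparison. The groups are small: at most 13 recruited to keep 10, an allowance of 3 per group. III.B excludes patients lost to follow-up and does not mention subjects who fail a review.

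**Working it through.** **1. The planned figure.** Inputs from III.B: 10 per group, improvements of 5%, 30% and 30%, SD 25%, alpha 0.05, one-way ANOVA.

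- Grand mean = (5 + 30 + 30)/3 = 21.67.
- Noncentrality = 10 × [(−16.67)² + 8.33² + 8.33²]/25² = 10 × 416.7/625 = 6.667.
- With 2 and 27 degrees of freedom, power = 0.581, against a stated 58%.

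The figure reproduces. Nothing in the review sentence enters it.

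**2. What a literal VAS rule could do.** A 30% improvement takes any baseline below 3/0.70 = 4.29 under the threshold. A 5% improvement does so only below 3/0.95 = 3.16. With the plan's means and SD, and percent reduction taken as normal, the chance that a single follow-up score is below 3 is:

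| Baseline VAS | Reduction needed | Test | Control |
|---|---|---|---|
| 4 | 25% | P(Z > −0.2) = 57.9% | P(Z > 0.8) = 21.2% |
| 5 | 40% | P(Z > 0.4) = 34.5% | P(Z > 1.4) = 8.1% |
| 6 | 50% | P(Z > 0.8) = 21.2% | P(Z > 1.8) = 3.6% |

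A simulation removed anyone below 3 at Visit 2 or 3 and analysed Visit 4. It assumed a 0-10 VAS, baselines between 3 and 10 of several shapes, one score per visit, and an effect either constant or building up over the visits.

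| Between-visit correlation | Removed, test | Removed, control | Retained difference (points) |
|---|---|---|---|
| 0 | 27-62% | 11-26% | 23.7-24.9 |
| 0.3-0.6 | 23-58% | 9-24% | 18.4-23.0 |
| 0.8 | 21-51% | 9-20% | 16.8-21.2 |

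Without removal the difference is 23.8-25.0 points. The result depends heavily on the assumptions. The protocol collects two VAS scores per visit (air and cold water), and III.D.1 does not say which must reach 3. If either score is enough, and assuming a common baseline and a correlation of 0.7 between the subject effects of the two stimuli, removal at between-visit correlations of 0.3-0.6 falls to about 9-37% of test subjects and 3-10% of controls.

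**3. Whether the protocol supports the literal reading.** Side by side:

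- *Assignment against exclusion.* III.F gives controls the product for the whole study, and III.B makes the comparison of the three groups the primary analysis. A generic review sentence cannot sensibly be read as ending the control arm at Visit 2.
- *Place of the criteria.* III.H.1 uses the inclusion and exclusion criteria to screen for enrollment. III.F at Visit 1 places qualification directly before randomization.
- *The withdrawal list.* Pregnancy and concurrent research appear both in the exclusion list and in III.D.3, each in a form suited to follow-up. Use of dental products is also restated there, as use of *other* products. The VAS threshold and prior desensitizing dentifrice were not carried over.
- *Order within the visit.* The review comes first; after it, "The same examiner from the initial visit will then conduct the oral exam and collect the sensitivity data". At Visit 2 the only score on file is the qualifying baseline. A VAS removal would need an old score carried forward to the next review, which no section describes. A Visit 4 score could remove nobody.
- *Consequence.* The criteria are to be reviewed. No section says that failing an entry criterion at that point means removal.
- *A natural purpose.* The sentence follows questions about changes in medical or dental history. It makes sense as a prompt to notice new conditions and withdrawal events.

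**The case for a change.** The best case for an amendment is that probable intent is not text. The sentence does name eligibility, the two criteria carry no time limit, and III.L says that deviations need prior IRB agreement. Some exclusions that are absent from the withdrawal list, such as milk allergy or dialysis, plausibly stay relevant during follow-up. Staff must therefore decide criterion by criterion which ones continue, after randomization and in very small arms. A clarification would cost a few words.

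The textual point stands: the protocol does not mark which criteria are entry-only. The harm does not follow from it. The dentifrice reading contradicts the trial's own assignment. The VAS reading also requires staff to set aside one entry criterion while enforcing another from the same section. For VAS, the withdrawal list is silent, which is not a contradiction. The non-compliance clause says only that a subject may be withdrawn, and it applies to all arms. How III.B treats withdrawn subjects is a fair question, but it arises whatever this sentence means and is a separate matter.

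**Conclusion.** No change is needed. The follow-up visits leave unstated which eligibility criteria continue after Visit 1. The assignment of the control product, the primary comparison, the enrollment wording and the separate withdrawal list all point the same way: the VAS threshold and the prior-dentifrice exclusion are entry conditions. Competent staff would apply them so.

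The loss of every adherent control is the result of a reading the protocol defeats, not a plausible size of effect. The 23-58% against 9-24% removal is hypothetical. It rests on an assumed VAS range, baseline distribution, time course, correlation and single score per visit, and on carrying scores forward. On the entry-only reading, the planned comparison and its 58% power stay as they are. A sentence of clarification would record the evident intent and would alter no figure or analysis. This conclusion assumes that staff follow the randomized assignment and the withdrawal list as written.
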